12.3. Analysis populations

All patients who sign an informed consent form and agree to undergo the battery of clinical examinations, imaging and laboratory tests specified in section 10 of the protocol, will be analysed in order to fulfil the objectives of the study.

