7.1. Inclusion criteria

Patient who participated in the APLICOV-PC study, who has been treated with plitidepsin and gives their consent.

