7.2. Exclusion criteria

There are no exclusion criteria for this study.

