2.10 Exclusion criteria

There are no exclusion criteria for this study.

3 General principles

Planned analyses in this document will be carried out once the database is declared cleaned, closed and approved by Pharma Mar according to the premises described in the Data Management Plan version 1.0 approved on 12-Jan-2022.

Statistical analyses will be performed using Statistical Analysis System (SAS) software version 9.4 and RStudio. The results of the analyses will be presented in editable format (i.e. rtf).

The data will be provided with one decimal place in general. In those cases where greater precision is required, as many decimal places as necessary will be provided.

Before performing the analysis, the following terms should be coded/reviewed and approved:

- Adverse events (AEs), hospital readmissions and COVID-19 complications. Coded according to Medical Dictionary for Regulatory Activities (MedDRA) and graded according to the National Cancer Institute Common Terminology Criteria for Adverse Events (NCI-CTCAE) v5.
- Medication. Classified according to the WhoDrug dictionary (latest version available).
- Reconciliation between the clinical database and the Pharmacovigilance database of serious adverse events (SAEs) in the study, including the resolution of all discrepancies.

Analysis will be done separately for each arm and the total population.

Continuous variables will be presented through the mean, median, standard deviation, range, first quartile (Q1) and third quartile (Q3). Categorical variables will be displayed through the distribution of frequencies and percentages; percentages with valid data will be presented and missing values will not be taken into account in the percentage calculation.

4 Imputation

There is no strategies/methods to handle missing data.

5 Study analysis populations

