5.1 Definition of the study population to be analyzed

All patients who sign an informed consent form and agree to undergo the set of clinical examinations, imaging and laboratory tests specified in section 10 of the protocol, will be analyzed in order to fulfil the objectives of the study.

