6.2 Patients characteristics

Demographic and baseline data:

- Age (years)
- Gender (male/female)
- Ethnic group (Arab; Caucasian; Latin; Asian; Black; Other)
- Weight (kg)
- Height (cm)
- Body surface area (BSA) (m²)
- Body mass index (BMI) - calculated

In addition to all the basal characteristics used in APLICOV-PC if it necessary.

7 Analysis of the primary endpoint

The main objective of the study is to evaluate the incidence of post-COVID-19 morbidity and characterize the profile of complications in the cohort of patients who participated in the APLICOV-PC study.

The number and percentage of patients who develop complications related to persistent illness, according to the physician, during the period between the end of the APLICOV-PC proof of concept study and the completion of this extension study by the patient, as well as the percentage of patients who present complications will be detailed.

A description of the following endpoints will be presented:

- Number and percentage of patients who required readmission to hospital and causes, since last visit of APLICOV-PC study until the end of this extension study.
- Number and percentage of patients who needed oxygen therapy and duration of the same, since last visit of APLICOV-PC study until the end of this extension study.
- The maximum, minimum, Q1 and Q3, mean, median and standard deviation (Std) of the duration of the oxygen therapy.
- Number and percentage of patients who presented complications (defined in Annex 5 of the protocol).
- Barthel Index. A description with the frequency and percentage of each dependency category, according to the score obtained, will be provided:
 - 0-20: Total dependency
 - 21-60: Severe dependency
 - 61-90: Moderate dependency
 - 91-99: Slight dependency
 - 100: Independence
- The maximum, minimum, Q1 and Q3, mean, median and Std of the parameters related to pulmonary function will be provided: oxygen saturation (SaO₂), ratio of partial pressure arterial oxygen and fraction of inspired oxygen (PAFI), forced vital capacity (FVC), forced expiratory volume in 1 second (FEV1), FEV1/FVC and diffusion test.

- The maximum, minimum, Q1 and Q3, mean, median and Std of the results of the Six-minute walk test (6MWT).
- Frequency and percentage of each category of the modified Medical Research Council (mMRC) scale:
 - 0 (Dyspnea only after strenuous exercise)
 - 1 (Dyspnea occurring when hurrying on level ground or walking up a slight incline)

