Hypertension				
Obesity				
Clinical status at baseline, n (%)				
Mild COVID-19 infection				
Moderate COVID-19 infection				
Severe COVID-19 infection				
Vital signs, median (range)				
Body temperature, $^{\circ}\text{C}$				
Systolic blood pressure, mmHg				

	Dose Cohort			
	Mild N=X	Moderate N=X	Severe N=X	Total N=X
Diastolic blood pressure, mmHg				
Heart rate, bpm				
Respiratory rate, bpm				
SpO ₂ at room air, %				
On oxygen at baseline, n (%)				
Laboratory parameters, median (range)				
WBC, x10 ⁹ /L				
Platelet count, x10 ⁹ /L				
Lymphocytes, x10 ⁹ /L				
Serum creatinine, µmol/L				
ALT, x ULN				
AST, x ULN				
LDH, x ULN				
GGT, x ULN				
CPK, x ULN				
Ferritin (ng/mL)				
D-dimer (ng/mL)				
C-reactive protein (mg/L)				
log ₁₀ viral load, median (range) copies/mL				
Days from Plitidepsin to first complication				
Days from hospital discharge to first complication				
Time from Plitidepsin first-dose to E- APLICOV inclusion (month)				

Table 12.12 Laboratory parameters

ECG Continuous endpoints	Dose Cohort																
	1.5						...						Total				
	N	Mean	Median	Range	Q1	...*	N	Mean	Median	Range	Q1
Hematology parameters																	
...																	
Coagulation parameters																	
...																	
Biochemistry parameters																	
...																	

* Q3 and Std.

Hematology: Basophils, Eosinophils, Hematocrit, Hemoglobin, Leukocytes, Lymphocytes, Monocytes, Neutrophils, Platelets.

Biochemistry: ALT, AST, Albumin, BUN, C-Reactive Protein, CPK, Calcium, Creatinine, Ferritin, GGT,

Glomerular filtrate, Glucose, LDH, Magnesium, Phosphatase alkaline, Potassium, Sodium, Total bilirubin, Troponin I, Troponin T.

Coagulation: Activated Partial Thromboplastin, D-Dimer, INR, Prothrombin Time

13 Other Listings

Listing 13.1 Hematological laboratory parameters

Dose	Subject id.	Date	Parameter	Value	Units	...(*)

*Range, grade, result and clinically significant

Listing 13.2 Coagulation laboratory parameters

Dose	Subject id.	Date	Parameter	Value	Units	...(*)

*Range, grade, result and clinically significant

Table 13.3 Biochemical laboratory parameters

Dose	Subject id.	Date	Parameter	Value	Units	...(*)

*Range, grade, result and clinically significant

14 ICH Listings

Following ICH E-3 guideline, patient listings will be performed.

- 16.2.1 Discontinued Patients
- 16.2.2 Protocol Deviations
- 16.2.3 Patients Not Included in the Efficacy Analysis
- 16.2.4 Demographic Data

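### The only analysis set requires agreement to the whole test battery, so a consenting patient who gives a complication history but declines the tests is left out of the primary incidence

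*Protocol*

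**What the plan says.** Protocol 12.3 sets two conditions for being analysed: "All patients who sign an informed consent form and agree to undergo the battery of clinical examinations, imaging and laboratory tests" listed in section 10. SAP 5.1 repeats them: patients who sign consent and "agree to undergo the set of clinical examinations, imaging and laboratory tests specified in section 10 of the protocol, will be analyzed". Neither document defines any other set.

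The entry rule is wider. Protocol 7.1 asks for a "Patient who participated in the APLICOV-PC study, who has been treated with plitidepsin and gives their consent", and 7.2 adds "There are no exclusion criteria for this study". Agreement to the tests is not an entry criterion.

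Other places bear on the same question:

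- Protocol 12.1 says that the final analysis takes in the total population of patients. SAP 6.1 describes patient characteristics on the full population.
- SAP Table 10.2 has separate Recruited and Analyzed columns, and SAP section 14 includes the listing "16.2.3 Patients Not Included in the Efficacy Analysis".
- SAP section 4 states "There is no strategies/methods to handle missing data", although Protocol 12.1 leaves the handling of unavailable data to the SAP. SAP section 3 bases percentages on valid data.
- Protocol 13.6 requires a reason in the eCRF when a variable is not available, and 13.8 requires evaluations not carried out to be stated there.

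**The concern.** The primary endpoint is the incidence of complications since the last APLICOV-PC visit. Annex 5 is a yes/no symptom list with dates and worst grade. Readmissions and oxygen therapy come from the history and are scheduled at baseline, before the test window. None of these needs the patient to walk, blow, give blood or be imaged.

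The analysis set nevertheless also asks for agreement to all of that. A consenting patient who answers the Annex 5 questions and then declines the tests is eligible and recruited but, followed literally, is analysed for nothing. Willingness to be tested could plausibly be related to sequelae, so the reported incidence would describe a self-selected part of a cohort that has at most 42 members and, under Protocol 8.2, no replacements.

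A smaller, related gap concerns the walk test, spirometry and diffusion. They are summarised on observed values only, and no table shows whether a missing value means that the patient was too ill to perform.

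**Working it through.** **1. The passages side by side**

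| Step | Condition | Source |
|---|---|---|
| Eligible | Earlier plitidepsin + consent | Protocol 7.1, 7.2 |
| Primary data available | Annex 5 history, readmissions, oxygen | Protocol 6.2, Annex 5 |
| Analysed | Consent + agreement to the section 10 tests | Protocol 12.3, SAP 5.1 |
| Final analysis | Total population of patients | Protocol 12.1 |

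A patient can meet the first two rows and fail the third, and rows three and four then disagree. The third row turns on agreeing, not on completing. A patient who agrees and then cannot perform a test still meets it.

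**2. The plan's own figures**

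Inputs from Protocol 12.2: maximum n = 42, null incidence 15%, alternative 5%, null rejected if 3 or fewer patients have complications, one-sided alpha 0.05, power 80%.

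Exact binomial: P(X ≤ 3) = Σ C(n,x) pˣ (1−p)ⁿ⁻ˣ for x = 0 to 3.

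- n = 42, p = 0.15: 0.107, against the stated alpha of 0.05.
- n = 42, p = 0.05: 0.843, against the stated power of 80%.

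The stated alpha is not reproduced. That is a separate matter; here 0.107 is the baseline for step 4.

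**3. Effect on the reported percentage**

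The documents give no number of refusers, so k below is an assumption, as is full enrolment of 42. One patient is 1/42 = 2.4%. Suppose 3 events are seen among those analysed:

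| k declining | Plan reports | All 42: no refuser affected | All 42: every refuser affected |
|---|---|---|---|
| 0 | 3/42 = 7.1% | 7.1% | 7.1% |
| 2 | 3/40 = 7.5% | 3/42 = 7.1% | 5/42 = 11.9% |
| 4 | 3/38 = 7.9% | 3/42 = 7.1% | 7/42 = 16.7% |

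The exact 95% interval is 1.7% to 21.4% for 3/38 and 7.0% to 31.4% for 7/42. The reported figure can lie above or below that for all 42, depending on who declines.

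**4. Effect on the rule of 3 or fewer**

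The rule is an absolute count, so removing patients can only leave the count unchanged or lower it. At a true incidence of 15%, with refusal unrelated to complications and the cut-off kept at 3:

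- n = 42: 0.107
- n = 40: 0.130
- n = 38: 0.158

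If refusal is related to complications the effect is larger. Assume 15% over all 42 and 50% among refusers. The analysed incidence is then (0.15 × 42 − 0.5k)/(42 − k):

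- k = 2: 5.3/40 = 13.3%, and P(X ≤ 3) = 0.21
- k = 4: 4.3/38 = 11.3%, and P(X ≤ 3) = 0.36

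**5. The function tables**

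Tables 11.6 and 11.9 carry an N per dose cohort, so the number of missing values can be worked out but the reason cannot. Listing 11.7 gives reasons for stopping or pausing, not for a test that was never done. Table 12.4 already has a row for whether the PCR test was performed, so the format exists.

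**The case against.** The strongest reply is that the group at issue may be empty. The tests are the substance of the study: Protocol 6.2 schedules them within 7 days of consent, so signing and agreeing may be a single act. The only listed reason for withdrawal is withdrawal of consent, and Protocol 13.6 then keeps only minimal data, so those patients would have no history to restore. This stands as far as it goes. But if the group is empty, the second condition does nothing and can be deleted; if it is not, the condition selects.

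A second reply is that Protocol 6.2 lists the tests under evaluation of the principal variable, that the primary count rests on a physician's judgement, and that Annex 5 has an open Others entry which tests could inform. Untested patients may therefore be slightly under-ascertained. This also stands, and is why the tested subset should be shown as well.

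A third is that the rule of 3 or fewer appears only in the sample-size paragraph. Protocol 12.1 calls the analyses mainly descriptive, and SAP section 7 contains no test against 15%. So the change in step 4 bears on the protocol's stated rule, not on a planned SAP output.

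A reader might also infer more than the documents support:

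- *Patients who cannot do the tests leave the primary incidence.* They do not, because the condition is agreement.
- *The most limited patients vanish from the function results.* Barthel, mMRC, SaO₂ and PAFI need neither walking nor blowing. The gap is confined to walk test, spirometry and diffusion.
- *Table 10.2 and listing 16.2.3 prove that refusers will be dropped.* The listing is a standard ICH E3 item, and the two columns would equally serve withdrawals of consent.

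**Conclusion.** The point holds for refusal. The only analysis set adds a condition that neither eligibility nor the primary history requires. As written, it leaves out a consenting patient who gives the history but declines the tests, and it is not reconciled with Protocol 12.1.

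How much this matters cannot be read from the documents. Under the assumption of 4 refusers among 42 and 3 events in the rest, 7.9% would be reported against a possible 7.1% to 16.7%. With no refusers there is no effect. It is tempting to say that the incidence is biased towards a healthier cohort. That is plausible but undocumented: patients who feel well may also decline tests, and the percentage would then be too high. What does not depend on direction is that an absolute cut-off of 3 never becomes harder to meet when patients are removed. The correction should be made because it is cheap and usable primary data in so small a cohort should not be set aside.

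**What to change.** - Define the primary set in Protocol 12.3 and SAP 5.1 as all consenting patients with Annex 5 information, whether or not they agree to the tests, and bring Protocol 12.1 into line.
- Show the incidence in the tested subset beside it, as a check on ascertainment.
- Keep each test summarised on patients with a result.
- For walk test, spirometry and diffusion (Tables 11.6, 11.7 and 11.9), add two rows by dose cohort: not done because unable for health reasons, and not done for another reason. Protocol 13.6 already requires reasons for unavailable variables, so no new data collection should be needed.

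The cost is wording in two documents, two rows in three table shells and one extra incidence line. N will differ between the primary and the test tables, and untested patients may have slightly less complete information under the open Others entry.

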12.4. Analysis of the primary endpoint

The main objective of the study is to evaluate the incidence of post-COVID morbidity and characterize the complications profile in the cohort of patients who participated in the APLICOV-PC study.

The number and percentage of patients who develop complications related to persistent illness, as judged by a physician, during the period between the end of the APLICOV-PC proof of concept study and the end of this extension study by the patient, as well as the percentage of patients who present complications.

A description of the following endpoints will also be presented:

- Number and percentage of patients who required readmission to hospital and causes, since last visit of APLICOV-PC study until the end of this extension study.
- Need for oxygen therapy and duration of the same, since last visit of APLICOV-PC study until the end of this extension study.
- The maximum, minimum, Q1 and Q3, mean, median and standard deviation of the duration of the oxygen therapy will be provided.
- Number and percentage of patients who presented complications (see annex 5).
- Barthel Index [\[26\]](#). A description will be provided with the frequency and percentage of each dependency category according to the score obtained:
 - 0-20: Total dependency
 - 21-60: Severe dependency
 - 61-90: Moderate dependency
 - 91-99: Slight dependency
 - 100: Independence
- The maximum, minimum, Q1 and Q3, mean, median and standard deviation of the parameters related to pulmonary function will be provided: SaO₂, PAFI, CVF, FEV1, FEV1/CVF and diffusion test.
- The maximum, minimum, Q1 and Q3, mean, median and standard deviation of the results of the 6 minute walk test will be provided.
- A description will be provided with the frequency and percentage of each category of the mMRC scale.
- Number and percentage of patients with abnormalities in the chest X-ray, in patients who present pneumonia upon entry into the APLICOV-PC study, and description of the abnormalities.
- Number and percentage of patients who presented abnormalities $\geq G2$ in the analytical parameters.
- Number and percentage of patients who presented abnormalities in the ECG, and description of the abnormalities.
- Number and percentage of patients who presented abnormalities in the heart Ultrasound/MUGA in patients who suffered a relevant cardiac event during their participation in the APLICOV-PC study, and description of the abnormalities.

The endpoints listed were correlated with the patients' basal characteristics, the degree of severity of the illness, comorbidities, the plitidepsin dosage, the viral load and the clinical evolution documented in the APLICOV-PC study.

13. DATA MANAGEMENT AND QUALITY ASSURANCE

13.1. Clinical trial monitoring and audits

The sites participating in the study will be supervised by monitors appointed by the sponsor, with specific training for this clinical trial, making periodic visits to the site before, during and at the end of the trial. These monitoring visits will be carried out in accordance with the International Council for Harmonisation (ICH) E6 (R2) guidelines. Visits can be supplemented by telephone contact or written communication. In this study, remote verification of source data may be performed in agreement with the participating centres.

Priority will be given to centralised monitoring and/or remote monitoring of the participating sites, avoiding overloading the site staff with tasks or reviewing source data and postponing, as far as possible, the verification of source data until it is possible to access the medical history directly. The sponsor will agree the conditions for such monitoring with the participating sites and teams.

Procedures will be established to ensure the quality of any aspect related to the trial.

13.2. Audits

During the clinical trial, the Quality Department of Pharma Mar S.A. or external auditors contracted by the sponsor may make audit visits to the site, either in person or remotely.

13.3. Inspections

Participation in this clinical trial implies acceptance of possible inspection by national or foreign regulatory authorities.

13.4. Reporting of serious breaches

Any serious breaches of the authorised protocol or of Royal Decree 1090/2015 that occur in Spain must be reported by the sponsor without undue delay and no later than seven calendar days from detection of the breach to the Spanish Agency for Medicines and Medical Products (AEMPS) and the CEIm.

For this purpose, a serious breach will be defined as any non-compliance that may significantly affect the safety and rights of the study subjects or the reliability and integrity of the data generated in the clinical trial.

Only serious breaches will be reported to the AEMPS and the CEIm, and breaches that do not constitute a serious breach will not have to be reported.

Each investigator has to document and explain in the clinical history of the subjects any breach to the approved protocol and/or Royal Decree 1090/2015. Investigators can implement a protocol breach to eliminate an immediate safety risk to the subject without prior CEIm approval, but such a breach must be reported to the study monitor within one business day. These incidents will be evaluated and, if appropriate, an amendment to the protocol will be prepared.

The monitor will document breaches during monitoring visits. The monitor will notify the investigator of the breach during the visit and the “Breach Form” document will be completed and signed by the investigator and monitor.

13.5. Data management

APICES will be responsible for processing and quality control of the data. Data management will be performed according to the Data Management Plan, standard operating procedures and the current regulations.

Data management based on Good Clinical Practice (GCP) standards refers to the activities defined to achieve safe routines for the efficient input of information in the study database, avoiding errors. Routines include procedures for CRF handling, application design and management, data entry and verification, data validation, database quality control and documentation of activities performed, including information on discrepancies found during the process. The database, data input screens and programming will be designed by APICES in accordance with the clinical trial protocol.

13.6. Electronic Case Report Forms (eCRF)

The collection of study data will consist of the electronic recording of all the information required by the eCRF. APICES will provide the eCRF.

All investigators agree to keep eCRFs filled in with truthful and accurate information as well as source documents that are part of medical records.

All the requested information must be completed in each patient's eCRF. If a patient is included in the study but withdraws their consent, only the minimal data will be collected in the CRDe, such as demographic data and the date of informed consent, as well as the reason for the withdrawal, if the patient does not mind providing it. In general, no queries will be issued for the data of these patients indicated in the eCRF as “Not done” or “Not available”.

For the patients included in the study, the information from the source documents will be included in each patient's eCRF by the staff of the investigation team of the site for this study and this information will be supervised by an APICES monitor. If the information requested on any variables is not available or does not apply, the reason must be included. Data should not be missing unless otherwise stated. Modifications to the eCRF must be made following the procedure described in the eCRF user guide and will be recorded in the eCRF.

Each completed eCRF must be reviewed, signed and dated by the Principal Investigator of the study without delay. The completed eCRF will be reviewed by the study monitor as soon as possible after completion. The site will be provided with an electronic copy of the final, approved and signed eCRF, which must be stored in the corresponding file.

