8. WITHDRAWAL AND DISCONTINUATION CRITERIA

8.1. Reason for withdrawal

Patients will be excluded or withdrawn from the study for any of the following reasons:

- Withdrawal of consent by the patient.

All cases of a patient's withdrawal from the study must be documented in the Case Report Form.

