1 The patient will sign the informed consent before undergoing any specific study procedure that is not part of normal clinical practice. 2 The patient must meet all the inclusion criteria in order to be included in the study. 3 It will be confirmed via a PCR test that the patient has no COVID infection at the moment of being recruited to the study. 4 The code assigned to the patient for participation in the (APLICOV-PC) reference study will be recorded. It will be confirmed if the patient has presented new COVID-19 episodes since the study ended, and if they have been vaccinated / the type of vaccine / received doses. Details of hospital readmissions and causes and the need for oxygen therapy were collected, from the last visit of the APLICOV-PC study to the signing of the informed consent form, and subsequently to the end of the study. 5 Vital signs: temperature, arterial tension, heart rate, respiratory rate. 6 Presence of complications (see annex 5) since the last visit of the APLICOV-PC study until the end of this extension study. 7 Evaluation of pulmonary function, including dyspnea evaluation (mMRC and 6 minute walk test) (annexes 7 and 9) SaO2, PAFl (direct or estimated) (annex 8), spirometry (forced vital capacity and FEV1) and the diffusion test. 8 The electrocardiogram: overall evaluation and measurement of PR, QT and RR intervals. Save the ECG in the patient's history. 9 Complete blood count, including inflammation markers. 10 It will include creatinine, ions, calcium, albumin, transaminases, bilirubin, alkaline phosphatase, LDH, CK, ferritin and troponin. 11 It will include D-dimer. 12 A chest X-ray will be taken for patients diagnosed with pneumonia upon admission to hospital, which led to their participation in the APLICOV-PC study. 13 A heart ultrasound / MUGA will be performed on patients who suffered a relevant cardiac event during their participation in the APLICOV-PC study. 14 All pharmacological treatments received by the patient since the last visit of the APLICOV-PC study to the signing of the informed consent form, will be collected. 15 Serious and non-serious adverse events related to the study procedures, from the signing of the informed consent until the end of the patient's participation in the study, will be collected. 16 If the patient so requested, their hospital readmissions/oxygen therapy, since the last visit of the APLICOV-PC study to the signing of the informed consent for the extension study, will be collected. 17 Collection of ultrasound images or the results of complementary (analytical or functional) tests necessary for interpreting post COVID-19 evolution.		

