5.4 End of study

The number and percentage of patients who completed or not the study will be provided. For those patients who finished the study early, the causes of termination will be described.

The cases considered as early termination are:

- Withdrawal of consent
- Follow up completed
- Lost to follow-up
- Death
- Other

All analysis will be performed separately for each arm and a total column will be added.

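### Protocol 13.6 limits the eCRF of a patient who withdraws consent to minimal data, so adverse events and complication history obtained before withdrawal may go unentered, in conflict with the collection rules and the analysis population

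*Protocol*

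**What the plan says.** Protocol 13.6 starts from a general rule: "All the requested information must be completed in each patient's eCRF". The next sentence makes an exception: if an included patient "withdraws their consent, only the minimal data will be collected in the CRDe, such as demographic data and the date of informed consent". The reason for withdrawal is added if the patient is willing to give it. Queries are in general not raised on such a patient's items marked as not done or not available.

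Withdrawal of consent is the only withdrawal reason in protocol 8.1, which adds: "All cases of a patient's withdrawal from the study must be documented in the Case Report Form". Section 8.2 allows no replacement.

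The rules on what is collected and analysed are elsewhere:

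- Evaluation calendar, footnote 15, covers "Serious and non-serious adverse events related to the study procedures, from the signing of the informed consent until the end" of the patient's participation.
- Footnote 6 covers "Presence of complications (see annex 5) since the last visit of the APLICOV-PC study until the end of this extension study". Section 6.2 asks for the same, and for readmissions and oxygen therapy over that period.
- Protocol 12.3 and SAP 5.1 analyse every patient who consented and accepted the tests. Neither removes a patient who later withdraws.
- SAP 5.4 expects early finishers to be reported: "For those patients who finished the study early, the causes of termination will be described".
- SAP section 4 gives no method for missing data, and SAP section 3 calculates percentages on valid data only.

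**The concern.** A patient can give a readmission and oxygen history at the consent visit, report complications, or have an adverse event during the tests, and then withdraw within the 7-day window. Footnotes 6 and 15 and section 6.2 call for that information. Section 13.6 gives the site a reason not to enter it.

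Two things are at stake. One is the adverse event record (SAP Tables 12.7 to 12.9 and Listing 12.8), which exists to show what the study procedures did to patients. The other is the primary endpoint, a proportion among at most 42 patients, where one record can matter. Two sites could also handle identical patients differently and each point to a section of the protocol in support.

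**Working it through.** The documents give no withdrawal rate and no figure that depends on one, so the check is mainly a comparison of the sections.

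**1. Does the exception reach data obtained before withdrawal?** It is defined by the type of patient (included, then withdrew), not by the period after withdrawal. Its two examples, demographics and the consent date, both exist before any withdrawal. If the sentence limited only later collection, there would be no need to list them. The list is open-ended, but adverse events and complication history are a different kind of item from the examples. A site has good reason to read the sentence as excluding them.

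**2. Does that conflict with other rules?**
- Adverse events: footnote 15 runs to the end of the patient's participation, so an event that begins before withdrawal is inside the rule.
- Complications, readmissions and oxygen therapy: these fall under footnote 6 and section 6.2, not the adverse event rule. Neither has a withdrawal exception.
- Analysis population: protocol 12.3 and SAP 5.1 keep the patient in, while 13.6 can leave that patient with no outcome.

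**3. Which safeguards remain?**
- Protocol 13.8 asks for entry during or soon after the visit, and 13.12 keeps an audit trail. These protect what has been entered. They do not say whether a site must still enter what is only in source documents when the patient withdraws.
- Protocol 11 sends effects possibly related to procedures to pharmacovigilance, with no exception for withdrawal. SAP section 3 then reconciles the two databases, but for serious adverse events only. A serious event missing from the eCRF should come to light there. A non-serious one has no stated route back into the tables.
- The query waiver in 13.6 means that, in general, blanks marked as not done or not available are not pursued.

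**4. What could one record do?** All counts here are assumed. Section 12.2 gives a maximum of 42 patients and rejects the 15% null if 3 or fewer have complications. Suppose 4 of 42 have them.

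| Case | Result | Meets the cut-off of 3? |
|---|---|---|
| All recorded | 4/42 = 9.5% | No |
| One affected patient withdraws, history not entered | 3/41 = 7.3% | Yes |
| One unaffected patient withdraws, history not entered | 4/41 = 9.8% | No |

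The denominator of 41 follows the SAP's valid-data rule. The percentage can move either way, depending on who withdraws.

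**The case against.** The best defence is that 13.6 is unclear rather than harmful. Its list of minimal data is introduced as examples, it orders no deletion, and it can be read as limiting collection once consent has gone. Prompt entry should put an event on day 3 into the eCRF before a withdrawal on day 4. The query waiver is general, not absolute, and covers only blank items. What happens to earlier data may be settled in the consent form or the Data Management Plan, neither of which is available here, and a limit on data may reflect participants' rights. The analysis is mainly descriptive (protocol 12.1), and SAP section 7 does not carry out the test behind the cut-off, so crossing it has no consequence laid down in the SAP.

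Most of this limits the size of the problem and should be accepted. It rules out three stronger readings that a reader might infer:

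- *That the data are certain to be lost, or that an event leading to withdrawal is never recorded.* The open list, prompt entry, the audit trail, the source documents, section 11 notification and the reconciliation of serious events all stand against this.
- *That the adverse event rule covers the complication history.* It does not. That half of the conflict is with footnote 6 and section 6.2.
- *That the bias is downward because harmed or burdened patients are the ones who leave.* This is plausible, but nothing in the documents shows it, and patients without symptoms may withdraw too.

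The defence does not remove the conflict itself. None of the safeguards tells a site to enter data it already holds for a withdrawn patient, and 13.6 points the other way.

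**Conclusion.** The point stands as a conflict between sections that should be resolved. Taken literally, 13.6 lets a site leave out adverse events and complication, readmission and oxygen-therapy data obtained before withdrawal, while footnotes 6 and 15 and section 6.2 require them and protocol 12.3 and SAP 5.1 analyse the patient. The exposure is greatest for non-serious adverse events.

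The effect on results cannot be sized. It depends on how many patients withdraw after giving data, whether their data had already been entered, and how each site reads the sentence. The 7-day window keeps the likely number small. Against that, the cohort is at most 42, withdrawn patients are not replaced, and there is no missing-data method, so even one record can count. The step from 4 of 42 to 3 of 41 shows only that; it is not a forecast.

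**What to change.** Replace the withdrawal sentence in protocol 13.6 with:

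> Data and adverse events obtained up to the date of withdrawal, including complication history, readmissions and oxygen therapy, are entered, retained and queried as far as the consent form and data-protection law allow; after withdrawal no further study data are collected except the reason, if volunteered.

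Add to SAP 5.1 that these patients stay in the complication and adverse event tables with the data they have. Notification under section 11 is unaffected.

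If a site has already applied the present sentence, the data can be entered from its source documents on the same terms.

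The cost is two sentences, a check that the consent form permits use of data obtained before withdrawal, and a few partial records and extra queries.
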